115	CHAPTER 12: MISCELLANEOUS CONSIDERATIONS.....	45
116	12.1 Prohibited Medications, Treatments, and Procedures	45
117	12.2 Participant Withdrawal.....	45
118	12.3 Confidentiality.....	45
119	CHAPTER 13: STATISTICAL CONSIDERATION	46
120	13.1 Statistical and Analytical Plans	46
121	13.2 Statistical Hypotheses	46
122	CHAPTER 14: DATA COLLECTION AND MONITORING	48
123	14.1 Case Report Forms and Device Data	48
124	14.2 Study Records Retention.....	48
125	14.3 Protocol Deviations	48
126	CHAPTER 15: ETHICS/PROTECTION OF HUMAN PARTICIPANTS	49
127	15.1 Ethical Standard	49
128	15.2 Institutional Review Boards	49
129	15.3 Informed Consent Process.....	49
130		

Protocol Summary

PARTICIPANT AREA	DESCRIPTION
Title	Safety of the Tandem t:slim X2 with Control-IQ Automated Insulin Delivery System in Preschoolers, age 2-6 Years Old.
Investigational Device	Tandem Control-IQ with G6 Continuous Glucose Monitor
Objectives	To assess study the safety profile of the Tandem t:slim X2 with Control-IQ system in children with T1D aged 2-6 years old under free living condition
Study Design	A single-arm, multi-center, clinical study
Number of Sites	3 independent clinical sites – sharing IDE and regulatory documentation only
Endpoint	Number of subjects with less than 6% time below 70 mg/dL and less than 40% time above 180 mg/dL.
Population	
Key Inclusion Criteria
 
 • Age ≥ 2 and < 6 years old at the time of visit 1 • Clinical diagnosis, based on investigator assessment, of type 1 diabetes for at least 3 months and using insulin at the time of enrollment • Use of an insulin pump in the past 3 months • Use of Dexcom G6 for at least 11 out of the last 14 days 
Key Exclusion Criteria
 
 • Hypoglycemia induced seizure or loss of consciousness in the past 3 months • Concurrent use of any non-insulin glucose-lowering agent • A condition, which in the opinion of the investigator or designee, would put the participant or study at risk.
Sample Size	Up to 15 participants
Participant Duration	About 14 days
Protocol Overview/Synopsis	48 hour hotel stay with 24/7 study team supervision followed by parental remote monitoring for 72 hours of at-home use

Study Visits and Procedures Schedule

	SCREENING	OPEN LOOP AT-HOME USE	PRE- ADMISSION CHECK-IN	HOTEL ADMISSION	CLOSED LOOP AT- HOME USE	POST- ADMISSION CHECK-IN
DURATION	ABOUT 3 HOURS		ABOUT 30 MINUTES	ABOUT 48 HOURS	ABOUT 72 HOURS	ABOUT 30 MINUTES

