224 The same system is also currently the subject of a similar trial down to 6 years old (IDE#20 above).

225 Finally, preliminary analysis of a clinical trial in France using the same system in prepubertal
 226 children (6-10 yo) comparing 24/7 vs overnight use has shown very promising performances as
 227 well (Table 1).

228

Table 1: Interim analysis of FREELIFEKIDS AP (N=30 for 3 months)

	Overall					
	CLC at night		CLC 24/7		Stats	
	baseline	CLC	baseline	CLC	base vs Tx	Night vs 24/7
% time below 50mg/dL	0.4 ± 0.3%	0.3 ± 0.2%	0.5 ± 0.7%	0.3 ± 0.2%	ns	ns
% time below 54mg/dL	0.7 ± 0.6%	0.6 ± 0.3%	0.9 ± 1%	0.5 ± 0.4%	0.081	ns

CLINICAL PROTOCOL

% time below 60mg/dL	1.5 ± 1%	1.1 ± 0.5%	1.7 ± 1.6%	1.1 ± 0.8%	0.041	ns
% time below 70 mg/dL	4.1 ± 1.9%	2.8 ± 1%	3.9 ± 2.8%	2.8 ± 1.9%	0.006	ns
% time between 70-140mg/dL	42 ± 8.6%	45.6 ± 7.4%	37.9 ± 8.2%	49.3 ± 4.9%	<0.001	0.009
% time between 70-180mg/dL	63.2 ± 9.1%	67.5 ± 6.5%	59.7 ± 8.4%	71.8 ± 4%	<0.001	0.009
% time above 180mg/dL	32.8 ± 9.2%	29.6 ± 6.7%	36.4 ± 9.5%	25.4 ± 4.8%	<0.001	0.010
% time above 250mg/dL	9.6 ± 4.3%	8.6 ± 3.7%	11.8 ± 5.6%	6.1 ± 2.2%	0.001	0.010
% time above 300mg/dL	2.8 ± 1.7%	2.7 ± 1.8%	3.9 ± 3.7%	1.7 ± 1%	0.030	0.046
Average CGM [mg/dL]	158.1 ± 13.6	156.7 ± 10.5	165.4 ± 15.8	150.2 ± 7.4	0.001	0.006

229 We propose to use the Control-IQ System during a supervised 48 hours hotel stay with planned
 230 activities and meals; in addition, child participants will continue to use the system for another 3
 231 days at home under the parent/guardian(s) supervision.

232 **1.3 Primary Specific Aim**

233 Study the safety profile of the Tandem t:slim X2 with Control-IQ System in children with type 1
 234 diabetes aged 2-6 years old.

235 **1.4 Secondary Specific Aims**

- 236 • Assess the safety profile of the system at home under parental/legal guardian(s)
 237 supervision
- 238 • Compare system performance to normative data from a 6-12 years old cohort

239 **1.5 Study Design**

240 **1.5.1 Purpose/Objectives of Clinical Study**

241 The purpose of this study is to demonstrate the safety and efficacy the Artificial Pancreas system
242 (Tandem t:slim X2 with Control IQ Technology) in T1D participants, aged 2-6 y.o.

243 **1.5.2 Study Participants**

244 Approximately 15 participants with Type 1 Diabetes Mellitus, currently managed with insulin
245 pump therapy, will participate in the trial for approximately 14 days. The study will be performed

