1068 Participation in the study is voluntary, and a participant may withdraw at any time. For participants
1069 who withdraw, their data will be used up until the time of withdrawal.

1070 **12.3 Confidentiality**

1071 For security and confidentiality purposes, subjects will be assigned an identifier that will be used
1072 instead of their name. Protected health information gathered for this study may be shared with the
1073 third party collaborators. De-identified subject information may also be provided to collaborators
1074 involved in the study after the appropriate research agreement has been executed.

1075 **Chapter 13: STATISTICAL CONSIDERATION**

1076 **13.1 Statistical and Analytical Plans**

1077 This trial is single-armed and not powered to detect differences between groups. The study is
1078 designed to obtain a primary safety profile on patients in this age-group.

1079 This study is an early feasibility study that will test the safety of t:slim X2 with Control-IQ
1080 Technology in an outpatient setting. These studies would generate up to 75 days of closed-loop
1081 data. This sample size allows for subject withdrawal.

1082 **13.2 Statistical Hypotheses**

1083 **13.2.1 Primary Outcome**

1084 Number of subject with less than 6% time below 70mg/dL and less than 40% time above
1085 180mg/dL.

1086 **13.2.2 Secondary Outcome**

- 1087 1. % time spent <70 mg/dl, <60mg/dl, <54mg/dL, and <50mg/dL
- 1088 2. % time spent >180mg/dl, and >250mg/dl, >300 mg/dl
- 1089 3. % time spent between 70-180mg/dl
- 1090 4. % time spent between 70-150mg/dl
- 1091 5. Number of hypoglycemia below 70 mg/dL
- 1092 6. Number of carbohydrate treatments, as well as total amount of carbohydrates used for
1093 treatments.
- 1094 7. Time spent in closed loop
- 1095 8. Time with available CGM
- 1096 9. Number of subject with more than 70% time in 70-180mg/dL range with less than 4%
1097 time below 70mg/dL

1098 **13.2.3 Success Criteria / Goal**

1099 As a general rule, a session will be considered useful for data analysis if the subject completes
1100 close to 80% of the active study protocol. Sessions are considered separate: (i) Supervised
1101 Phase=complete at least 38 hours of AP; (ii) at home use=complete at least 56 hours of AP.

1102 *The primary goal will be considered met if the primary outcome is achieved for 65% or more of
1103 the subjects.*

1104 **13.2.4 Statistical Analysis Plan**

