1105 Proportions of subject matching primary criteria will be computed and directly compared to 65%
1106 (considered baseline). Further analysis will be performed using a chi² test of goodness of fit. Based
1107 on prior data in 6-12 year olds we anticipate a possible effect size of 0.64, which would allow to
1108 detect a difference with 70% power considering our sample size.

CLINICAL PROTOCOL

1109 Overall outcomes will be compared to the normative data below (values derived from the analysis
1110 of 30 6-12 year old T1D subjects using pumps and CGM and rounded for ease of use):

	Baseline	
	mean	std
% time below 50mg/dL	0.5%	0.5%
% time below 54mg/dL	1%	0.8%
% time below 60mg/dL	2%	1%
% time below 70 mg/dL	4%	2.5%
% time between 70-140mg/dL	40%	9%
% time between 70-180mg/dL	60%	9%
% time above 180mg/dL	35%	9%
% time above 250mg/dL	11%	5%
% time above 300mg/dL	4%	3%
Average CGM [mg/dL]	162.0	15.0

1111 This analysis will be performed using a single group one sided t-test for mean comparison for
1112 outcomes that can be assumed normally distributed and One-Sample Wilcoxon Signed Rank test
1113 for median comparison for the others, this analysis is not powered.

1114 Secondary outcomes will be reported for the entire period and for the supervised and home phases
1115 separately. Outcomes by phase will be compared to each other to assess possible loss of
1116 performances during the transition at home. For this purpose, McNemar's tests will be used to
1117 compare the supervised phase to the home phase for the primary outcome and secondary outcome
1118 # 6, 7, and 8. All other outcomes will be analyzed using repeated measure ANOVA. Significance
1119 of 0.05 will be used.

1120 This analysis is not powered.

1121 **Chapter 14: DATA COLLECTION AND MONITORING**

1122 **14.1 Case Report Forms and Device Data**

1123 The study data are collected through a combination of case report forms (electronic and paper) and
1124 electronic device data files obtained from the software and individual hardware components.
1125 These electronic device files and electronic CRFs are considered the primary source
1126 documentation.

1127 When data are directly collected in electronic case report forms, this will be considered the source
1128 data. Records will be maintained in accordance with ICH E6 and institutional regulatory
1129 requirements for the protection of confidentiality of participants.

1130 **14.2 Study Records Retention**

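### The comparison with the 6-12 year old cohort uses one-sample tests that ignore the cohort's sampling error, and calls for a median test without naming a null value

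*Combined protocol and SAP*

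**What the plan says.** Section 1.4 sets the second secondary aim: "Compare system performance to normative data from a 6-12 years old cohort". Section 13.2.4 carries it out. A table headed Baseline lists ten CGM metrics with two columns, mean and standard deviation, derived from an analysis "of 30 6-12 year old T1D subjects using pumps and CGM and rounded for ease of use".

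The tests are described in one sentence: "This analysis will be performed using a single group one sided t-test for mean comparison for" "outcomes that can be assumed normally distributed and One-Sample Wilcoxon Signed Rank test" "for median comparison for the others, this analysis is not powered". The Protocol Summary gives the trial size as "Up to 15 participants".

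The table prints no median, and the text gives no null value for the Wilcoxon test. It does not list which outcomes count as normal. One-sidedness is attached to the t-test only, and its direction is not given. The 0.05 level comes at the end of the separate paragraph comparing the supervised and home phases, directly after "All other outcomes will be analyzed using repeated measure ANOVA. Significance".

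**The concern.** A one-sample test takes its reference value as a known constant. Here that value is an estimate from 30 children, and the SD and sample size needed to express its uncertainty are printed but not used. If the question is whether these children differ from that cohort, the standard error is too small and a difference is declared too often.

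The second difficulty is the median test. A sponsor following the text has only a mean to test against. For a right-skewed, non-negative outcome the median lies below the mean, so using the mean as the null would push the test toward a result of lower than the cohort. For time in hypoglycemia or marked hyperglycemia, that result favours the device. Pointed the other way, the same test would rarely detect an increase.

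At stake is the reading of the second secondary aim. Section 13.2.4 is the only place where an analysis for that aim is specified.

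**Working it through.** The plan states no power, error rate or interval for this comparison, so there is no figure to reproduce. The 70% power in Section 13.2.4 belongs to the primary outcome.

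**Inputs.** Trial n = 15 (Protocol Summary, as a maximum). Reference n = 30, with means and SDs from the table in Section 13.2.4. Alpha = 0.05 is an assumption for this comparison. All error rates assume that the trial children share the reference distribution.

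**1. Reference treated as exact (normal outcomes, equal SDs).**

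- The planned standard error is SD/√15. The correct one for a two-cohort difference is SD·√(1/15 + 1/30). The ratio is √(1 + 15/30) = 1.225.
- For time in 70-180 mg/dL (SD 9): 9/√15 = 2.32 points against 9·√(1/15 + 1/30) = 2.85 points.
- True one-sided error: P(t₁₄ > 1.761/1.225) = 8.6%. At n = 13 the same formula gives 8.1%.
- Sensitivity to equal SDs at n = 15: if the trial SD is 0.75 times the reference SD the error is 11.0%; if 1.5 times, 6.7%.
- If the tabulated value is a fixed constant by definition, the error is 5%.

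**2. Which rows look skewed.** A percentage of time cannot be negative. A normal distribution with the printed mean and SD would put an appreciable share below zero in four rows, and in each the mean minus 2 SD is negative:

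| Row (mg/dL) | Mean, SD (%) | Mean − 2 SD | Share below zero if normal | Implied median (lognormal / gamma) |
|---|---|---|---|---|
| below 50 | 0.5, 0.5 | −0.5 | 15.9% | 0.35 / 0.35 |
| below 54 | 1, 0.8 | −0.6 | 10.6% | 0.78 / 0.80 |
| below 70 | 4, 2.5 | −1.0 | 5.5% | 3.39 / 3.49 |
| above 300 | 4, 3 | −2.0 | 9.1% | 3.20 / 3.28 |

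The lognormal median is mean/√(1 + (SD/mean)²), for example 0.5/√2 = 0.35. Two nearby rows do not meet the criterion: below 60 gives 2 − 2 = 0, and above 250 gives 11 − 10 = 1. They are left out of the figures below.

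**3. Wilcoxon test if the printed mean is taken as the null.** These are simulated exact one-sided signed-rank tests at n = 15 (attainable size 4.7%), with no reference error included. Ranges run from gamma to lognormal for the two columns toward lower, and from lognormal to gamma for the column toward higher. The third column is a one-sided t-test against the correct mean, which shows what skewness alone does at this sample size.

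| Row | Wilcoxon, toward lower | t-test against the correct mean, toward lower | Wilcoxon, toward higher |
|---|---|---|---|
| below 50 | 16.8-22.8% | 11.8-15.4% | 0.4-0.9% |
| below 54 | 13.8-18.8% | 10.4-13.2% | 0.7-1.2% |
| below 70 | 11.1-15.0% | 8.9-11.2% | 1.1-1.8% |
| above 300 | 12.9-17.7% | 9.9-12.6% | 0.9-1.4% |

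Toward lower, the error is therefore about 11-23%, of which about 9-15% is already present from skewness. The gap between the two tests is about 2 points (11.1 − 8.9) to 7 points (22.8 − 15.4). Toward higher, the error is about 0.4-2%, so the test would be insensitive to harm. If the Wilcoxon test is two-sided, the total error for these rows is about 7-15%.

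**4. Would printing a median be enough?** No. The signed-rank test also assumes symmetry. Tested against the true median of these skewed shapes, it rejects about 2-3% toward lower and about 9-13% toward higher.

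**5. Size of the correction.** For 70-180 mg/dL, the planned 95% half-width is 2.145 × 9/√15 = 4.98 points. Welch with n = 30 (df 28.1) gives 2.048 × 2.85 = 5.83. At n = 13 the figures are 5.4 and 6.2.

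**The case against.** The plan calls the values normative data and rounds them for convenience, which is how one treats a fixed yardstick. On that reading the one-sample t-test holds its 5% level. This stands as a condition on the 8.6%. However, Section 1.4 ties the data to a cohort, and nothing in the documents justifies the figures as performance goals.

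The sponsor derived the table from an analysis of 30 children and may hold the medians. This also stands. A reader might infer that the plan as written tests a median against a mean and so favours the device. The text does not say that. It leaves the null value and the direction open, and the 11-23% applies only if the mean is used and the test points toward lower.

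A reader might also infer that rounding moved the benchmarks in the device's favour, by matching the table to the interim results in Table 1 of Section 1.2. The documents do not identify Table 1 as the source, and it covers ages 6-10 rather than 6-12. No effect of rounding is claimed here.

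Finally, the study is an early feasibility study and the analysis is declared not powered. That limits the weight, but lack of power concerns missed differences and does not excuse an understated standard error.

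**Conclusion.** Wrong as written, minor in weight. For the cohort comparison named in the second secondary aim, the planned tests use a standard error that is too small by a factor of 1.225 at n = 15 with equal SDs. The t-test's true one-sided error is then 8.6% in place of 5%, assuming alpha 0.05 and normal outcomes.

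The Wilcoxon branch is incompletely specified: no null value, sidedness, direction or alpha. The t-test's direction is missing too. The Wilcoxon error rates above are conditional on the mean being the null, on the direction and on the assumed shapes; they show what the gap could allow, not what the plan prescribes. Confidence is high for the wording gap and the t-test arithmetic, and lower for the Wilcoxon rates.

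The 65% primary goal is not affected, and no stated decision rests on these p-values.

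**What to change.** In Section 13.2.4, replace the one-sample tests with a Welch two-sample comparison that uses the reference mean (unrounded if the sponsor holds it), the reference SD and n = 30. Report each difference with a two-sided 95% confidence interval, and describe it as a comparison with an older cohort.

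Do not test a median against a printed mean. For skewed outcomes, use a two-sided Wilcoxon rank-sum test if the 30 individual reference values are held. Otherwise give the Welch interval only, and note that its tails are unequal under skew: about 3-5% on the device-favouring side and about 1-2% on the other, against a nominal 2.5% each (simulated at n = 13 and 15). State sidedness, direction where relevant, alpha, and which outcomes go to which method.

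The cost is SAP wording and a slightly wider interval: for 70-180 mg/dL, a half-width of 5.8 in place of 5.0 points at n = 15. The Welch comparison needs nothing beyond what is printed. The rank-sum test needs individual data that the documents do not show the sponsor to hold.

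### In the hotel-versus-home comparison, McNemar's test is assigned to three secondary outcomes (#6, #7, #8) that are counts, amounts or durations with no cut-point, so it cannot be run on them as written

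*Combined protocol and SAP*

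**What the plan says.** Section 13.2.4 reports secondary outcomes for the whole period and by phase, then compares the phases to look for worse performance after the move home: "performances during the transition at home. For this purpose, McNemar's tests will be used to" "compare the supervised phase to the home phase for the primary outcome and secondary outcome" numbers "6, 7, and 8. All other outcomes will be analyzed using repeated measure ANOVA". The significance level is 0.05, and the section closes by saying that the analysis is not powered.

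Section 13.2.2 defines the outcomes concerned. Outcome #6 is "Number of carbohydrate treatments, as well as total amount of carbohydrates used for" treatments, #7 is "Time spent in closed loop", and #8 is time with CGM data available. Outcome #9 counts children with more than 70% of time in 70-180 mg/dL and less than 4% of time below 70 mg/dL.

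The only hour limits in the statistical chapter are in section 13.2.3: "As a general rule, a session will be considered useful for data analysis if the subject completes" close to 80% of the active protocol, which is spelled out as "Phase=complete at least 38 hours of AP; (ii) at home use=complete at least 56 hours of AP".

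For a different analysis, the comparison with normative values, section 13.2.4 uses a t-test for "outcomes that can be assumed normally distributed and One-Sample Wilcoxon Signed Rank test" for the rest.

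**The concern.** McNemar's test works on a paired two-by-two table and uses only the children whose yes/no status differs between phases. A count, a number of grams or a number of hours does not produce such a table until someone sets a cut-point. The plan sets none for #6, #7 or #8, so the analyst would have to choose either a cut-point or a different test, possibly after seeing the data.

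Carbohydrate treatments, closed-loop use and CGM availability bear directly on whether performance is lost when supervision passes to the parents, and home safety under parental supervision is a secondary aim (section 1.4). These are the measures left without a usable phase test.

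A related gap is scaling. Outcomes #1 to #4 are percentages of time. Outcomes #5 to #8 are worded as numbers, totals or times, with no statement of how they are adjusted for phases of different length.

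**Working it through.** **1. Plan's own figure.** No number is attached to the phase comparison. The only power figure in section 13.2.4 is 70% for the goodness-of-fit test of the primary outcome. With n = 15, effect size 0.64, 1 degree of freedom and alpha 0.05, the noncentrality is 15 × 0.64² = 6.144 and the power is 0.698, so that figure reproduces. It does not concern this point.

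**2. Outcome type against assigned phase test** (definitions from 13.2.1 and 13.2.2, tests from 13.2.4).

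| Outcome | Value per child per phase | Assigned test | Can it be run as written? |
|---|---|---|---|
| Primary | yes/no | McNemar | yes |
| #1-#4 | % of time | ANOVA | yes |
| #5 | count | ANOVA | yes, scaling unstated |
| #6 | count, and an amount | McNemar | no |
| #7 | duration | McNemar | no |
| #8 | duration | McNemar | no |
| #9 | yes/no | ANOVA | yes, but differs from the primary outcome |

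Three of nine secondary outcomes, or four measures because #6 has two, have no usable phase test.

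**3. Can the 38 h and 56 h limits serve as cut-points?** They equal 38/48 = 79% and 56/72 = 78% of the nominal phases, in line with the stated 80%. Their stated job is to decide whether a session is usable, and they say nothing about #6 or #8. If they were applied strictly and also used as the cut-point for #7, all analysed children would be yes in both phases. With 15 children the table is 15 yes/yes and 0 elsewhere, with no discordant pairs and no information.

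**4. Does the choice of another cut-point matter?** In one invented set of 15 paired closed-loop durations (illustration only), the discordant pairs and exact two-sided p-values were:

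- cut at 85% of phase length: 6 against 2, p = 2 × (1 + 8 + 28)/256 = 0.29
- cut at 90%: 5 against 3, p = 2 × (1 + 8 + 28 + 56)/256 = 0.73
- cut at 95%: 4 against 3, p = 1.00

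The same data give different answers depending on a choice that the plan leaves open.

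**5. Outcome #9 under ANOVA.** With two phases, repeated-measures ANOVA is a paired t-test. Suppose k of 15 children change, all in the same direction. Exact McNemar gives p = 2 × 0.5^k. For ANOVA with k = 4, the mean difference is 4/15 = 0.267, its SD is √(15/14 × 0.267 × 0.733) = 0.458, and t = 0.267/(0.458/√15) = 2.26 on 14 df.

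| k | ANOVA p | Exact McNemar p |
|---|---|---|
| 4 | 0.041 | 0.125 |
| 5 | 0.019 | 0.0625 |
| 6 | 0.009 | 0.031 |

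At k = 4 or 5 the two tests fall on opposite sides of 0.05, so the primary outcome and #9 would be judged by different standards although they are the same type of data.

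**6. Time scale.** Nominal phases are 48 h and 72 h (Protocol Summary), and 72/48 = 1.5. On the timetable in sections 5.4 and 5.6, arrival at 3-5 pm on day 1 to the end of lunch at 12:30 pm on day 3 is 45.5 to 43.5 h, which gives 72/45.5 = 1.58 to 72/43.5 = 1.66. With identical hourly performance, unscaled home totals would exceed hotel totals by about these factors.

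**The case against.** The best case for leaving the plan alone is that little depends on it. This is an early feasibility study, the phase comparison is declared unpowered, and every outcome is reported by phase whatever test is used. The error is also plain: it would stop an analyst rather than silently produce a wrong answer. All of that stands, and it sets the rank of the point.

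The numbering may simply be a slip, since the one yes/no secondary outcome is #9. That is plausible, but the documents do not confirm it, and a slip would still need correcting.

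The argument about the 38 h and 56 h limits should not be pressed too far. Section 13.2.3 presents them as a general rule, and section 12.2 keeps withdrawn children's data up to withdrawal. The absence of discordant pairs therefore holds only if the rule is applied strictly. In either case the plan does not offer the limits as cut-points.

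ANOVA on #9 can be computed and is not invalid in itself. The objection to it is inconsistency with the primary outcome.

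A reader might also infer that the comparison is set to report false deterioration at home. Under assumed Poisson event rates of 0.25 to 3 per day, equal in both phases, simulation of unscaled counts for #5 gives false-positive rates of 12% to 80%. The documents do not support that as a finding. They give no event rates and do not say that raw totals will be compared. It illustrates why the scale should be stated, and no more.

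**Conclusion.** The point holds at low rank. As written, McNemar's test cannot be run on secondary outcomes #6, #7 and #8, which is 3 of 9 secondary outcomes and 4 measures. This follows from the definitions alone and needs no assumption. Outcome #9 is assigned to a different test from the primary outcome although both are yes/no per child. The need for a common time scale for #5 to #8 follows from the nominal 48 h and 72 h phases. The factor of about 1.5 applies only if raw totals were compared, on which the plan is silent.

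A reader might infer that the trial's main conclusion is at risk. It is not: McNemar's test suits the primary outcome, and the 65% goal, the sample size and the by-phase descriptive reporting are unaffected. What is lost is a pre-specified test of the move home for carbohydrate treatments, closed-loop time and CGM availability.

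**What to change.** In section 13.2.4, replace the sentence assigning McNemar's test and the sentence assigning ANOVA with:

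> McNemar's exact test will compare the supervised and home phases for the primary outcome and secondary outcome #9. Outcome #5 will be expressed per 24 h of available CGM time, outcome #6 (number of treatments and grams of carbohydrate, separately) per 24 h of elapsed phase time, and outcomes #7 and #8 as percent of elapsed phase time, where elapsed phase time runs from Control-IQ activation to discharge (supervised) and from discharge to the end of home use (home). Outcomes #5 to #8 will be compared between phases with the paired Wilcoxon signed-rank test. Outcomes #1 to #4 will be analyzed using repeated measure ANOVA.

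The signed-rank test is already the plan's choice for non-normal outcomes in the normative comparison, so no new method is introduced. If the sponsor prefers McNemar's test for #6 to #8, a cut-point for each of the four measures must be fixed before the data are seen.

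The cost is a few sentences of SAP text and no extra participants or visits. The times of Control-IQ activation, discharge and end of home use must be on record for each child. The comparison remains unpowered at 15 children, and the text should continue to say so.
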